#### 6.3 Participant exclusion criteria

Individuals with current dermatitis as diagnosed by a medical practitioner, individuals who have used topical steroid cream to their hands in the past six weeks, visiting or temporary personnel who are undertaking duties on NHS premises including students on placements,

NHS Foundation Trust

contractors and anyone not directly employed by the participating NHS organisation. Individuals on long term sick leave (4 weeks or longer)

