# 7 STUDY PROCEDURES

#### 7.1 Screening Procedures

With the assistance of Trust departmental managers and occupational health services, we will identify a minimum of six departments at each site where staff are known to engage in frequent hand washing and therefore have an increased occupational risk of dermatitis. As above, these departments will comprise a mix of patient-facing areas (wards) and other clinical settings (laboratories and mortuary).

In collaboration with departmental managers and with the support from local occupational health departments and Clinical Research Network (CRN) research delivery staff, we will distribute an information flyer (poster) to promote the study to eligible staff working in the selected departments. The study manager will work with clinical leads (department/ward managers) to develop a targeted approach to ensure participants' engagement with the study. This will include promotion of the study at team meetings, in the OH department and in communal staff rooms followed by provision (sent by the clinical leads via email) of an electronic participant information sheet (PIS) which will contain a link (including QR code) to the secure REDCap (eCRF) data collection portal.

A non-probability (convenience) sampling approach will be used to screen and recruit participants to the study. Accordingly, the study will be promoted to all staff from each participating department/unit.

No personal information will be reviewed or screened during the process of promoting the study to staff. If staff are interested in taking part, they will be encouraged to access study material (additional copy of the participant information sheet and consent form) via the online questionnaire platform using the link in the PIS or by using the study's QR code printed on posters and flyers. Note: Study documents (PIS, consent form and questionnaire) will be made available in Welsh upon request.

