#### 7.2 Participant recruitment

We aim to recruit 1386 participants across our three participating sites (~460 at each site). Staff interested in taking part will simply need to follow the link which will invite them to complete the online study screening for eligibly questions to ascertain their eligibility for inclusion into the study. To motivate staff to participate in the study, especially those concerned about job security if problems with hand dermatitis are identified, we will emphasize the potential benefits of our questionnaire, and guarantee the confidentiality of participants' information received.

We have followed the HRA guidance on 'Proportionate approach to seeking consent' when devised the following e-consent method. Those screened as eligible for the entry into the study will be asked to complete an online e-consent form via the eCRF (REDCap) portal before completing the self-assessment skin surveillance screening questionnaire. Importantly, prospective participants will be free to access the study Redcap portal at a time of their

choosing during the recruitment period. Participants will not be able to access their questionnaire once completed.

In addition, with the participants' consent we will collect NHS email addresses of participants and their line manager, to enable notification of assessment outcome.

At the end of the e-consent participants will be required to tick a box to confirm that "I certify that all of my information in the document is correct. I understand that clicking 'submit' will electronically sign the form and that signing this form electronically is the equivalent of signing a physical document".

After completing and electronically signing the e-consent form (form 1), participants will be given the option to click on a hyperlink which takes them directly to the Part 2 (form 2) of the questionnaire.

Participants will then be assigned a unique participant identification number (PIN) when logging into the portal.

Based on our previous work (5, 13,19) we anticipate that the recruitment period will need run for up to nine months.

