By taking part in this study, participants will be provided with a remote digital assessment of hand dermatitis based on the data they provide (i.e. hand photographs). Therefore, if this assessment indicates that they may have hand dermatitis then we will recommend that they self-refer for follow-up advice and support from either their local occupational health, GP or pharmacist. Conversely, where applicable, participants may also benefit by receiving confirmation that they do not have hand dermatitis.

At the end of the questionnaire, participants will have the option to enter a prize draw to win a gift voucher. In total, there will be twenty £50 shopping vouchers available to win. Winners will be chosen at random. To be eligible to win this prize, participants will need to have completed the questionnaire, provided their hand photographs and a valid NHS email details.

Since we are testing digital methods for skin surveillance, paper-based study documentation will not be included in this study.

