## **12 STATISTICAL CONSIDERATIONS**

The following outlines the proposed statistical analyses methods planned as they relate to each research question (RQ).

• RQ1 Can a self-assessed hand dermatitis screening questionnaire for at-risk health care workers reliably be used as part of a health surveillance programme?

As the primary study outcome, we will calculate the sensitivity of the proposed selfassessment screening tool (single-item self-reported dermatitis) along with its 95% confidence intervals when compared with the gold standard (nurse's dermatitis assessment from the hand photographs). We will further assess its specificity, positive and negative predictive value. The analysis will be conducted for all participants and then separately by medium and high risk of hand dermatitis, determined by frequency of hand washing 10-20 times per day (medium risk), and more than 20 times per day (high risk).

• RQ2 What is the sensitivity and specificity of the hand dermatitis self-assessment screening questionnaire in identifying early hand dermatitis, and is it similar across all Fitzpatrick skin phototypes and occupational (clinical vs non-clinical) groups?

The accuracy of hand dermatitis self-assessment screening questionnaire will further be explored in sub- groups of our sample participants. Primarily sensitivity, and specificity, and further positive and negative predictive values, as indicators of the accuracy of the screening test will be estimated for clinical and non-clinical staff and their differences will be compared statistically. Due to the high number of NHS staff of non-white ethnic origin, and the lack of information about hand dermatitis or ability to self-report its presence across the six Fitzpatrick skin phototypes, we will also stratify our results by Fitzpatrick phototypes, with a potential to identify skin phototypes in which accuracy of the screening questionnaire is lower.

• RQ3 Is the self-assessment screening questionnaire and photographic method acceptable and feasible to use in healthcare staff in a busy NHS setting?

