#### **NHS Foundation Trust**

# **17 REPORTING AND DISSEMINATION**

#### 17.1.1 Potential relevance to policy and practice

If the findings from this study indicate that the single-item questionnaire with follow-up of those reporting possible hand dermatitis using teledermatology (selfie hand photographs taken with a mobile phone camera) is feasible, acceptable, and effective as a self-assessment screening tool in a workplace surveillance programme then we envisage the findings will have important relevance to policy and clinical practice of skin health surveillance programmes in the health service.

Most notably, the potential to implement this self-assessment screening tool more widely across the NHS workforce and to other high-risk worker groups will lead to improvements in the early detection and management of workers hand dermatitis, and such favourable outcomes will have wider benefits to the NHS. We are evaluating the health surveillance tool in the health service setting for pragmatic reasons, but since we are testing the tool in non-clinical staff, there is no reason why the results should not be generalisable to other industries such as care homes, hairdressing, and floristry where workers also have a high risk of developing hand dermatitis.

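### Positive and negative predictive values are to be tested between clinical and non-clinical staff as accuracy, although they also move with a prevalence that this sample does not fix

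*Protocol*

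**What the plan says.** Section 12.1 of the protocol makes sensitivity the primary outcome, with specificity and the two predictive values (PPV and NPV) as secondary outcomes. Under RQ1, after sensitivity, Section 12 says: "We will further assess its specificity, positive and negative predictive value". It repeats that analysis in medium-risk and high-risk strata defined by daily hand washing. Under RQ2, sensitivity and specificity come first. The sentence then goes on to "positive and negative predictive values, as indicators of the accuracy of the screening test will be estimated for clinical and non-clinical staff" and ends with "their differences will be compared statistically". That ending covers all four measures.

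Three other places bear on prevalence in the sample. Section 7.1 says: "A non-probability (convenience) sampling approach will be used to screen and recruit participants to the study". Section 6.3 excludes, among others: "Individuals with current dermatitis as diagnosed by a medical practitioner, individuals who have used topical steroid cream to their hands in the past six weeks". Section 12.1 assumes 15% prevalence and hypothesises that it is the same in clinical and non-clinical staff.

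Section 17.1.1 argues that, because the tool is being tested in non-clinical staff, "there is no reason why the results should not be generalisable to other industries such as care homes, hairdressing, and floristry".

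**The concern.** Sensitivity is calculated among people with dermatitis and specificity among people without it. PPV and NPV are calculated among those who answer positive or negative, so they combine accuracy with the share of the group that has the condition. Two staff groups can recognise dermatitis on their own hands equally well and still differ in PPV because one has more of it.

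A statistical comparison of PPV, labelled as accuracy, can therefore lead to the conclusion that self-assessment works less well in one group when it does not. RQ2 exists to answer exactly that question. The risk strata under RQ1 raise the same issue of interpretation: they are chosen to differ in dermatitis risk, so their PPVs should differ even at identical accuracy, although no test is stated there.

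The protocol does not limit sample PPV and NPV to the people recruited, and Section 17.1.1 extends the results to other industries without distinguishing measures that depend on prevalence.

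**Working it through.** **The plan's own figure.** Section 12.1 gives sensitivity 0.90, lower bound 0.80, prevalence 15% and 231 per group. With a half-width of 0.10:

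- cases needed = 1.96² × 0.90 × 0.10 / 0.10² = 34.57
- participants = 34.57 / 0.15 = 230.5, rounded up to 231
- total = 6 × 231 = 1386; per staff group = 3 × 231 = 693

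The stated 231 and 1386 are reproduced.

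**Inputs for the check.** Sensitivity (Se) 0.90 and 693 per staff group come from Section 12.1. Specificity (Sp) is not given; 0.90 is assumed and 0.80 is shown beside it. The prevalences 17% and 13% are the ICU-nurse and student-nurse figures in the Introduction. They illustrate a plausible gap and are not estimates for clinical and non-clinical staff. The protocol names no test, so a pooled two-proportion z-test at two-sided 5% is assumed.

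**Formulas**, with prevalence p:

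- PPV = Se·p / [Se·p + (1 − Sp)(1 − p)]
- NPV = Sp(1 − p) / [Sp(1 − p) + (1 − Se)p]

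**Dependence on prevalence, Se 0.90:**

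| Prevalence | PPV, Sp 0.90 | NPV, Sp 0.90 | PPV, Sp 0.80 |
|---|---|---|---|
| 5% | 0.32 | 0.994 | 0.19 |
| 10% | 0.50 | 0.988 | 0.33 |
| 15% | 0.61 | 0.981 | 0.44 |
| 25% | 0.75 | 0.964 | 0.60 |

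**Two staff groups with equal accuracy, Sp 0.90:**

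- 17%: PPV = 0.153 / (0.153 + 0.083) = 0.648, with about 693 × 0.236 = 163.5 positive answers
- 13%: PPV = 0.117 / (0.117 + 0.087) = 0.574, with about 693 × 0.204 = 141.4 positive answers
- pooled PPV = 0.270 / 0.440 = 0.614; standard error = √[0.614 × 0.386 × (1/163.5 + 1/141.4)] = 0.056
- expected z = 0.075 / 0.056 = 1.34; chance of exceeding 1.96 = P(Z > 0.62) ≈ 0.27

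Simulation of 40,000 studies per scenario agrees. The table shows how often each test declares a difference:

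| Prevalence in the two groups | Sp | PPV | NPV | Se | Sp test |
|---|---|---|---|---|---|
| 15% v 15% | 0.90 | 5% | 5% | 5% | 5% |
| 17% v 13% | 0.90 | 27% | 11% | 5% | 5% |
| 17% v 13% | 0.80 | 36% | 11% | 5% | 5% |
| 20% v 10% (assumed) | 0.90 | 92% | 43% | 5% | 5% |

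Only the PPV and NPV tests react to prevalence. The tests of sensitivity and specificity keep their 5% error rate throughout.

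**The case against.** The protocol ranks the measures correctly. RQ2 asks only about sensitivity and specificity, the analysis sentence opens with them as primary, and predictive values are secondary outcomes. Reporting PPV and NPV from a cross-sectional sample is ordinary practice. Section 12.1 hypothesises equal prevalence in the two staff groups, and if that is true the comparison is neutral. A statistical analysis plan could hold a table over prevalences. Section 17.1.1 is dissemination text and governs no analysis.

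Most of this stands, and it limits the point. It does not remove it: the protocol itself calls predictive values accuracy and plans the comparison, and the equal prevalence is a planning assumption that nothing in the design secures.

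Some stronger readings are tempting but not supported:

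- **That recruitment inflates PPV.** A reader might infer from "By taking part in this study, participants will be provided with a remote digital assessment of hand dermatitis" that staff with hand problems will come forward. The same section expects reluctance, "especially those concerned about job security if problems with hand dermatitis are identified", and answers it with a confidentiality guarantee. The study is promoted to all staff in each department, and the prize draw is open to anyone who completes it. The net direction is unknown.
- **That excluding known cases is a mismatch with the programme.** The protocol does not say whether already diagnosed staff would be screened with this question. A programme limited to undiagnosed staff would share the exclusion.
- **That sample PPV will set the programme's workload.** No section says so; the stakeholder forum is only to consider the findings.

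**Conclusion.** The point holds for the secondary outcomes and for one sentence of Section 17.1.1. Comparing PPV and NPV between clinical and non-clinical staff as accuracy can produce a false finding of unequal accuracy. At 17% against 13% prevalence the chance is about 27% for PPV (36% if specificity is 0.80) and about 11% for NPV, where 5% is intended. It rises to about 92% for PPV at an assumed 20% against 10%, and falls to the nominal 5% if prevalence is equal. These figures rest on an assumed specificity, an assumed test, illustrative prevalences, and 693 assessable participants in each staff group.

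The PPVs by hand-washing stratum under RQ1 need the same caution in reading. The claim about other industries is too strong: the staff listed as examples in Section 6.2 are NHS nurses, operating department practitioners, and mortuary and laboratory staff, and predictive values do not carry over to a setting with a different prevalence. The primary outcome and the sample size of 1386 are not affected.

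**What to change.** In Section 12:

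- Limit the statistical comparison of accuracy between groups to sensitivity and specificity, and stop describing PPV and NPV as accuracy there.
- Report sample PPV and NPV descriptively, each beside the prevalence in that group or risk stratum, labelled as applying to volunteers without a current diagnosis.
- Add PPV and NPV calculated from the estimated sensitivity and specificity over a stated prevalence range, for example 5% to 25%. Note that sensitivity and specificity may themselves differ in a population that includes diagnosed or treated staff, so this table does not remove every limit on transfer.

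In Section 17.1.1, replace the claim about other industries with a statement that those settings need their own evaluation.

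The cost is wording and one table computed from estimates already planned, with no added participants or data. The downside is that predictive values become conditional on prevalence and the dissemination claim is narrower.

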# 4 TRIAL OBJECTIVES AND PURPOSE

#### 4.1 Research Questions

1. Can a self-assessed hand dermatitis screening questionnaire for at-risk healthcare workers reliably be used as part of a health surveillance programme?

2. What is the sensitivity and specificity of the hand dermatitis self-assessment screening questionnaire in identifying early hand dermatitis, and is it similar across all Fitzpatrick skin phototypes and occupational (clinical vs non-clinical) groups?

3. Is the self-assessment screening questionnaire and photographic method acceptable and feasible to use in healthcare staff in a busy NHS setting?

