#### 12.1 Statistical power

Considering as the primary study outcome the sensitivity of the single-item questionnaire (with secondary outcomes being its specificity, positive and negative predictive value) we enquired six occupational physicians with experience in NHS work what they would consider as the minimum acceptable sensitivity for such a self-assessment screening tool (single-item questionnaire) to be administered by managers to detect hand dermatitis in at risk healthcare workers. The majority (3 out of 4 who responded to our enquiry) reported a sensitivity of 80%. Assuming a prevalence of hand dermatitis among healthcare workers of 15%, and a high sensitivity of 0.90% with a width of confidence interval 0.10 (targeting a lower bound for sensitivity of 0.80), the estimated required sample size is 231. We hypothesised the same prevalence for clinical and non-clinical staff, and also for staff of light, medium and dark skin. This totals 1386 participants (i.e. 231 participants for each of the 6 groups clinical/non-clinical staff and type of skin), which would give sufficient power for any analysis stratification. We aim to recruit approximately equal numbers (~460 participants) from each of the 3 sites in the study.

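### Research question 2 asks whether accuracy is similar across phototypes, but section 12 plans a statistical comparison only for staff groups and merely stratifies by phototype

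*Protocol*

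**What the plan says.** Protocol section 4.1 puts both factors into one question about sensitivity and specificity: "is it similar across all Fitzpatrick skin phototypes and occupational (clinical vs non-clinical) groups". Section 12 then gives a method for each factor.

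- **Staff group.** Accuracy measures "will be estimated for clinical and non-clinical staff and their differences will be compared statistically".
- **Phototype.** The reason given is lack of information on hand dermatitis or on the "ability to self-report its presence across the six Fitzpatrick skin phototypes". The method is to "stratify our results by Fitzpatrick phototypes, with a potential to identify skin phototypes in which accuracy of the screening questionnaire is lower".

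The phototype sentence mentions no comparison between phototypes. Confidence intervals are stated explicitly for the primary sensitivity, "along with its 95% confidence intervals when compared with the gold standard", and are not mentioned again for the strata.

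Section 12.1 sizes the study for the precision of a single sensitivity estimate in six cells. Those cells are staff group (two) by light, medium or dark skin (three), not the six phototypes. It concludes that power is adequate for every stratified analysis.

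**The concern.** Whether accuracy is similar across groups is a question about differences. Six separate estimates do not answer it, however carefully each is made. The protocol recognises this for staff group and, in the next sentence, does not for phototype. An analysis that follows the text could report six sensitivities, point to the lowest, and never assess whether the spread exceeds what chance produces.

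The phototype half carries the equity aim set out in the Introduction, that the tool should work equally well on all skin types. Two errors are possible: a phototype may be described as poorly served when it is not, or a real difference may go unassessed.

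**Working it through.** **1. Inputs**
- Total sample 1386, six cells of 231 (section 12.1).
- Prevalence: "Assuming a prevalence of hand dermatitis among healthcare workers of 15"%.
- Assumed sensitivity and precision: "a high sensitivity of 0.90% with a width of confidence interval 0.10". This is read as 0.90 with a lower bound of 0.80, the target the same sentence gives.
- Minimum acceptable sensitivity 0.80: "The majority (3 out of 4 who responded to our enquiry) reported a sensitivity of 80"%.
- Number of phototypes: six (section 12).
- Assumption, not in the protocol: cases split evenly over the phototypes. Section 7.1 plans convenience sampling and no phototype quota is stated.

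**2. The plan's own figure**
- Cases per cell = z² × p(1 − p) / d² = 1.96² × 0.90 × 0.10 / 0.10² = 34.57.
- Participants per cell = 34.57 / 0.15 = 230.5, rounded up to 231. Six cells: 6 × 231 = 1386.

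The figure reproduces with 0.10 as the half-width. It is a one-sample precision calculation and does not address differences between groups.

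**3. Cases per phototype**
- 1386 × 0.15 = 207.9, about 208. Divided by six: 34.65, about 35.
- 95% interval with 35 cases at 0.90: 0.90 ± 1.96 × √(0.09/35) = 0.90 ± 0.099, or 0.80 to 1.00.

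**4. Spread when nothing differs**

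Simulation of 200,000 studies with 35/35/35/35/34/34 cases and true sensitivity 0.90 in all six:

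| Event | Share of studies |
|---|---|
| Some phototype ≥5 points below the other five combined | 82% |
| Best-to-worst gap ≥10 points | about 70% |
| Some phototype ≥10 points below the other five combined | 27% |
| Any estimate below 0.80 | 16% |

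The median best-to-worst gap is about 12 points and the median lowest estimate is 0.83.

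The last row can be checked exactly. An estimate is below 0.80 with 27 or fewer positives out of 35 (probability 0.0200) or out of 34 (0.0481). So 1 − (1 − 0.0200)⁴ × (1 − 0.0481)² = 0.164.

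**5. Sensitivity to the assumptions**
- The 5-point figure is about 61% at a common sensitivity of 0.95, 90% at 0.85 and 93% at 0.80.
- With an uneven split (10/50/60/40/30/18 cases, assumed) it stays at about 82% at 0.90.

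**6. What a comparison would deliver**

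Approximate rejection rates at the 5% level:

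| True pattern | Global test, 5 df | Trend test |
|---|---|---|
| All 0.90 | 5% | 5% |
| Phototype VI at 0.80, others 0.90 | 20% | 21% |
| Phototype IV at 0.70, others 0.90 | 62% | 5% |
| Linear fall, 0.95 to 0.80 | 35% | just over 60% |

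Both tests control false positives. The trend test gains power for a steady gradient but does not detect one poorly served phototype in the middle of the scale. For scale, separating 0.80 from 0.90 between two groups with 80% power needs 199 cases per group, against about 35 expected.

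These figures concern sensitivity. Specificity would rest on more people, 1386 × 0.85 / 6 = about 196 per phototype. The protocol assumes no value for it, so none is simulated here.

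**The case against.** The phototype sentence is exploratory and hedged. It sets no ranking rule and no threshold, and it does not forbid a comparison. If the strata are reported with intervals, as the primary sensitivity is, a span of 0.80 to 1.00 would make the overlap plain. The choice of test, adjustment and criterion is normally left to a statistical analysis plan, which is not available here.

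Much of this stands. A reader might infer that phototypes will be singled out by ranking point estimates. The text does not say so. A reader might also infer that a phototype will falsely look worse in most studies. That holds for a 5-point shortfall or a 10-point range, but not for a 10-point shortfall (27%) or for the protocol's own 0.80 benchmark (16%). An estimate below 0.80 becomes common (69%) only if the true sensitivity is 0.85 throughout, which is not what section 12.1 assumes. Nor do the documents require phototype to be analysed as an ordered scale. The Introduction mentions difficulty of recognition in skin of colour, but it also asks for equal performance in all phototypes, and section 12 cites a lack of information across all six.

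What does not stand is the argument that this is only missing detail. Section 12 states a method for each half of the same question and gives a comparison to one half only. An analysis plan written to match could properly contain no phototype comparison.

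**Conclusion.** The point holds as a mismatch between research question 2 and its stated analysis. The phototype half has no comparison, so following section 12 as written cannot establish whether accuracy is similar across phototypes. The chance figures show why the strata should not be read by eye, and each must be quoted with its criterion. They rest on 15% prevalence, full recruitment of 1386 with assessable photographs, an even split over phototypes and a common sensitivity of 0.90. The text does not support a claim that the phototype result will be mainly noise or that a false finding is planned. This should be corrected before analysis, and it does not affect the primary estimate of overall sensitivity.

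**What to change.** In section 12, add after the phototype sentence wording such as:

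*Sensitivity and specificity will also be compared statistically across the six phototypes by a global test of homogeneity, for example logistic regression of the self-assessment result on phototype among reference-positive participants and, separately, among reference-negative participants. Estimates for each phototype, their 95% confidence intervals and confidence intervals for differences will be reported. A trend test over the ordered scale will be supplementary. No phototype will be described as having lower accuracy on the ranking of point estimates alone, and a non-significant result will not be taken to show similarity.*

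The global test comes first because the stated aim is to find any phototype in which accuracy is lower, and a trend test alone would not detect an isolated one.

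The cost is a change of wording and two regression models on data already planned for collection. The drawback is low power, about 20% for the global test if one phototype is truly 0.80 and the others 0.90. That figure should stand beside the result, and the general assurance of power in section 12.1 should not be taken to cover this comparison.
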